10.4 PROTOCOL AMENDMENT HISTORY

The table below is intended to capture changes of IRB-approved versions of the protocol, including a description of the change and rationale. A Summary of Changes table for the current amendment is located in the Protocol Title Page.

Version	Date	Description of Change	Brief Rationale

Appendix S1 - A SAS macro for Implementing the Bayesian Multiple Imputation	
Method	57
Appendix S2 - Sample SAS Code for PROC MIANALYZE	65

LIST OF ABBREVIATIONS

The following abbreviations will be used within this SAP.

Abbreviation or special term	Explanation
400MW	400-meter walking test
6MWT	6-minute (distance) walk test
AE	Adverse Event
AESI	Adverse Event of Special Interest
ALM	Appendicular Lean body Mass
ALT	Alanine Aminotransferase
ANCOVA	Analysis of Covariance
AST	Aspartate Aminotransferase
ATC	Anatomical Therapeutic Chemical
b.i.d	Twice a day
BMI	Body Mass Index
CFR	Code of Federal Regulations
CIRS	Cumulative Illness Rating Scale
CI	Confidence Interval
cm	Centimetre
CMH	Cochran Mantel-Haenszel
CNS	Central Nervous System
COVID-19	COronaVIrus Disease 2019
CRF	Case Report Form
CSR	Clinical Study Report
DEXA	Dual Energy X-ray Absorptiometry
DNA	Deoxyribonucleic Acid
DSMB	Data Safety Monitoring Board
ECG	Electrocardiogram
eCRF	Electronic Case Report Form
EU	European Union
FAS	Full Analysis Set
ICH	International Conference on Harmonisation

Version Final 2.0, Date: 04JUN2021

kg	Kilogram
LS	Least-squares
MAR	Missing at Random
MedDRA	Medical Dictionary for Regulatory Activities
MI	Multiple Imputation
MMRM	Mixed Model for Repeated Measurements
OR	Odds Ratio
PAT-D	Pepper Assessment Tool for Disability
PF-10	10 item Physical Function domain at SF-36
PK	Pharmacokinetics
PRO	Patient Reported Outcome
РТ	Preferred Term
SAE	Serious Adverse Event
SAP	Statistical Analysis Plan
SARA	SAR copenia and sarcopenic obesity in patients Aged \geq 65 years
SarQoL	Sarcopenia Quality of Life (questionnaire)
SAS	Statistical Analysis System
SD	Standard Deviation
SF-36	Short Form-36 (quality of life questionnaire)
SF-MNA	Short Form Mini-Nutritional Assessment
SOA	Schedule of Activities
SOC	System Organ Class
SCPT	Stair Climb Power Test
SPPB	Short Physical Performance Battery
TEAE	Treatment Emergent Adverse Event
TFLs	Tables, Figures and Listings
TSD-OC	Test SIO Disabilità Obesità Correlata (obesity disability questionnaire)
US	United States
WHODDE	World Health Organization Drug Dictionary Enhanced

1 INTRODUCTION

The purpose of this Statistical Analysis Plan (SAP) is to provide detailed descriptions of the statistical methods, data derivations and data displays for study protocol BIO101-CL03, Version 1.2.11, titled "Safety and Efficacy of BIO-101 175 mg b.i.d. and 350 mg b.i.d. 26-week oral administration to patients suffering from age-related SARcopenia, including sarcopenic obesity, Aged \geq 65 years and at risk of mobility disability. A double-blind, placebo controlled, randomized INTerventional Clinical Trial (SARA-INT)" dated 18Oct2019 for final analysis. The list of Tables, Figures and Listings and templates for the TFLs will be produced in a separate document.

Any deviations from this SAP will be described and justified in the Clinical Study Report (CSR).

The preparation of this SAP has been based on International Conference on Harmonization (ICH) E3 and E9 guidelines $^{(1, 2)}$.

All data analyses and generation of TFLs will be performed using Statistical Analysis System (SAS®) version 9.3 or higher.

The statistical analyses plan (SAP) will be finalized & signed-off before database lock and unblinding.

2 STUDY OBJECTIVES

2.1 Primary objective

The primary objective of this study is to evaluate the effects of two daily doses of BIO101 versus placebo on mobility functions as measured by the gait speed during the 400-meter walking (400MW) test.

2.2 Secondary objectives

The key secondary objectives of this study are:

- To evaluate the effect of BIO101 on physical function from the study subjects' perspective using an adapted patient reported outcome (PRO).
- To evaluate the effect of BIO101 on muscle strength using the handgrip strength test.

The other secondary objectives of this study are:

- To assess changes in body composition and specifically on appendicular lean body mass (ALM), which is an expression of sarcopenia.
- To estimate the change of 400MW test as a dichotomous variable, for possible use in further studies.
- To evaluate the effects of two daily doses of BIO101 versus placebo on mobility functions as measured by the distance measured during the 6 minutes walking test.
- To estimate the effect on muscle strength.
- To assess the overall change of the SPPB total score as a cumulative expression of the physical frailty status.
- To assess muscle functions using a simplified function test, i.e. the change in time needed to complete the chair stand test.

• To estimate the effect using a sarcopenia-specific PRO, in preparation of future studies.

3 STUDY DESIGN

3.1 General study design

This study is a three arm (2 doses versus placebo), randomized, double-blind, placebo-controlled parallel design phase 2 clinical trial, with total study duration of 33-35 months.

This comparative clinical trial evaluates the effects of a 6-month treatment duration, based on the hypothesis that physical function of sarcopenic, older subjects with an initial degree of mobility disability (SPPB≤8) will be meaningfully improved after 6 months of oral treatment with BIO101 (in at least one of the two tested doses) with respect to placebo.

This multi-site study will enroll 231 community dwelling older adults (men or women \geq 65 years) reporting a loss of physical function over the previous 6-12 months and considered at risk of mobility disability to undergo screening tests for inclusion in the study. Included subjects will be randomized in a 1:1:1 ratio, for one of the 3 arms of treatment in a blinded manner.

Safety of study patients and investigators should be the priority during COVID-19 outbreak. Only ePROs (SF36, SARQoL, TSD-OC and Pat-D) will be assessed during this period until further guidance. An extension of the treatment period for a total period of 9 months of intervention will enable the full assessment of the safety and efficacy of the investigational product for a significant part of the population randomized in this study, while staying in compliance with good clinical practice (GCP), and minimizing risks to trial integrity during the COVID-19 pandemic.

Bias are minimized by the use of identical therapeutic units whose number is automatically assigned via an eCRF embedded algorithm after the Investigator confirms randomization of a subject. The Study Flow Chart is presented in **Figure 1**.

3.2 Randomization and blinding

At each study center, subjects who are eligible to enter the double-blind treatment period will be randomized to one of the three treatment arms (BIO101 175mg, BIO101 350mg or placebo), in a 1:1:1 ratio through by Randomization will be stratified by gender and study center.

The staff at the study center, the Sponsor and its representatives, and all subjects will be blinded to the identity of the investigational product.

The DSMB will be unblinded for the DSMB reviews. Full unblinding of the study will occur after database lock unless there is medical emergency. The study blinding may only be broken for an individual subject in the case of an emergency where the investigator considers it essential to know what treatment the subject was receiving. The monitor shall be notified promptly if a treatment code envelope is opened. It is recommended that the Investigator contacts the Sponsor before opening an envelope, if possible. The Investigator must document the date, time, and reason for the unblinding in the patient's medical records.

Should the code be (intentionally or unintentionally) broken by the Investigator or by someone on the clinical staff, the subject could remain in the study or not, as judged by the Investigator, according to the patients' best interest. The event will be immediately reported to the Sponsor and to dealt as a major protocol deviation. The clinical data for this patient will not be included in the analysis of the Per Protocol population.

3.3 Study treatments and assessments

The maximum study duration from screening to end of study is 32 months.

There will be three treatment groups in this study.

- 175mg BIO101 bid
- 350mg BIO101 bid
- Placebo

All included subjects will complete the inclusion visit and start a 6 to 9-month treatment and observation phase, with the main evaluation at the end of the study duration. Based on non-clinical considerations, the exposure is capped at 39 weeks.

A detailed description of procedures and assessments to be conducted during this study is summarized in SOA in Protocol section '1.3 SCHEDULE OF ACTIVITIES (SOA)'

Page 14 of 69

4 STUDY ENDPOINTS

4.1 Primary endpoint

The primary endpoint of this study is Change from baseline to month 6 (M6)/month 9 (M9) in 400MW gait speed.

4.2 Secondary endpoints

The key secondary endpoints of this study are:

- Change from baseline to M6/M9 in Physical Function Domain (PF-10) sub-score of the Short Form Health Survey (SF-36)
- Change from baseline to M6/M9 in Handgrip strength test

The other secondary endpoints of this study are:

- Change from baseline of ALM and other parameters of body composition based on DEXA
 measurements
- The rate of success to complete 400 meter walking test after the 6-month/9-month treatment versus placebo
- Change from baseline of the distance during 6 Minute Walking Test (6MWT) distance
- Change from baseline in muscle strength based on the knee extension and the SCPT
- Change from baseline of the SPPB total score
- Change from baseline of the time for five chair stands as part of the SPPB assessment
- Change from baseline using the SarQol auto-evaluation questionnaire
- Change from baseline in PAT-D.
- Change from baseline in TSD-OC for obese patient
- Change from baseline in SF36 (total score)

4.3 Safety data

The safety data for this study is:

- Adverse Events (AEs)
- Clinical laboratory data (haematology, biochemistry, coagulation, urine analysis)
- Vital signs
- Physical examinations
- Electrocardiograms ECGs

Ī		
•		

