 - M9 visit must be scheduled 39 weeks after Day 0. This end of intervention visit can be scheduled before M9 in case of patient withdrawal or based on modification of public health emergencies and the core consensus guidelines for clinical trial management.
 - All safety and efficacy measurements previously listed for the M6/end-ofintervention visit are to be performed.

- M10.5 phone call
 - Post study intervention phone call 6 weeks after the end of intervention visit to follow up on safety parameters

	Screening -8 – 0	Randomization & Baseline Visit Day 0	M1 Visit 4		M3, M	Post study Intervention Phone Call			
Weeks				12	21	26	32	39 (or End of intervention)	45 (6 weeks after end of intervention)
Visit Window	n.a.	n.a.	+/-3 days	+/- 1 week	+/- 1 week	- 1 week	+/- 1 week	8 weeks	+/- 1 week
Telephone call			Х	Х	Х	x	Х		X
Informed consent, including secondary research	X (before any study activity)								
Informed consent (2) for biobank and DNA tests	X (before any study activity)								
New informed consent, including secondary research			Xf	Xf	Xf	X£			
Demographics	X (4 weeks)								
Medical history	X (4 weeks)								
Concomitant medication review	х		х	x		x		X	
Physical exam & Anthropometry	х	х						X	
Safety measurements including vital signs and weight		х						x	
SPPB	X (4 weeks)							X	
ECG	X (1 week)								

Version 1.2.11, 20 April 2020

DEXA	Х		,				Х	
Gallbladder ultrasound	х						х	
Hematology ²	X (1 week)						Х	
Biochemistry ¹	X (1 week)						Х	
Urinalysis ³ (dipstick)	X (1 week)						х	
Plasma and urine collection for biomarkers	X (1 week)						x	
400MW test	X (no earlier than 48 hrs before Day 0)						Х	
Inclusion/ Exclusion criteria	х							
Randomization		Х						
CIRS		Х						
SF-MNA		Х						
6 MWT		Х					 Х	
Stair Climb Power Test		Х					 х	
Grip strength		Х					Х	
Knee extension (optional)		х					х	
SF-36		Х		X	Î	Х	Х	
PAT-D		Х				X	Х	
SarQoL		Х		X		Х	Х	
TSD-OC		Х		X		Х	Х	
Deliver investigational treatment		х	x	x		x		

Collect used treatment & record compliance to study intervention			х	x		х		Х	
Actimetry*		Provided	Х	Х				collected	
General safety questions			х	х	Х	х	х		х
AEs review and evaluation		x	х	х	х	х	х	х	х
Diabetes/ prediabetes questions							х		х
POP-PK sampling (optional)		X (1 day after Day 0)						х	
eCRF completion	Х	Х	Х	Х	Х	Х	Х	Х	Х

Date of each next visit should be calculated back on Day 0 visit (baseline) in order to not exceed the total duration of 26 weeks of treatment (capped exposure).

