7 STUDY INTERVENTION DISCONTINUATION AND PARTICIPANT DISCONTINUATION/WITHDRAWAL

7.1 DISCONTINUATION OF STUDY INTERVENTION

The Investigator should discontinue study intervention and specifically ensure that a participant stops taking the investigational drug if the bioanalytical results at Month 1 or Month 3 shows the following changes:

1. Confirmed 3-fold or greater elevations above the Upper Limits of Normal (ULN) of

These stopping rules for discontinuation are established based on

Discontinuation from investigational oral treatment does not mean discontinuation from the study, and remaining study procedures should be completed as indicated by the study protocol. If a clinically significant finding is identified (including, but not limited to, changes from baseline) after enrollment, the investigator or qualified designee will determine if any change in participant management is needed. Any new clinically relevant finding will be reported as an AE.

The data to be collected at the time of study intervention discontinuation will include the following:

- AE complete follow-up (if the treatment is stopped following an AE)
- Last investigational medication administration date and time

The physician can decide to re-introduce the investigational treatment if it was stopped because of a concomitant acute condition he/she considers unrelated to the treatment.

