8.2 SAFETY AND OTHER ASSESSMENTS

Several procedures and evaluations in SARA-INT clinical protocol will be performed to monitor the study intervention's safety. Some of those are necessary for other purposes (e.g., screening, eligibility, and enrollment).

• **Physical examination:** a standard medical exam of all organ systems to detect possible concomitant conditions that could represent an exclusion criterion (e.g. food ulcer, lower limbs arterial insufficiency, severe respiratory condition, etc.)

- **Anthropometry**: includes height and weight, subcutaneous tissue thickness (with the help of a plicometer) and various circumference measurements
- Short Form -Mini Nutritional Assessment (SF-MNA): this is a 6-question short form of the MNA that can be completed in 5 minutes or less. The MNA has been validated in international studies with a broad range of HCPs in a variety of settings. Currently, this instrument is administered by healthcare professionals to determine patients' nutritional status (Huhmann et al, 2013)⁶¹
- Vital signs (pulse and blood pressure) are measured at screening, M1, M3 and M6 (or endof-study) visits. These are measured twice, in lying or sitting and standing positions
- Electrocardiograms (ECGs): this is performed for screening purposes only. It will be read locally, in order to exclude any underlying cardiac diseases that could represent an exclusion criteria. Meaningful abnormalities will be reported on the eCRF. The original will be kept in the source documents. This should be conducted prior to the start of any physical functional assessments (e.g. the 400MW test) for the safety of the study participants
- Radiographic or other imaging assessments: 1) DEXA scan in SARA-INT is mostly devoted to assess body composition in terms of appendicular lean body mass, at screening visit and M6 (or end-of-study visit). DEXA scans could be performed up to 8 weeks before randomization and enrollment. 2) Gallbladder ultrasound: this is required during screening to exclude previous or active hepatobiliary diseases (e.g. cholestasis/biliary tract obstruction, cholelithiasis, cholecystitis, etc.), and is repeated at the end of the treatment (M6 visit) to assess any emergent hepatobiliary abnormalities

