9.4.5 SAFETY ANALYSES

Safety variables will be summarized/analyzed by groups of treatment, on the Safety population.

Vital signs, biochemistry and hematology parameters will be described by descriptive statistics, for the entire period of the study and at each timepoint.

Usual tables (by SOC and preferred term) will be produced for AEs (falls, injurious falls and orthostatic hypotension will be tabulated separately) after coding with the MEDRA terms.

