8.8 Safety analyses

All analysis of safety data will use the Safety population.

All safety data will be summarized/analyzed by treatment group.

No statistical hypothesis testing will be performed.

Due to the COVID-19 situation and safety concerns over viral transmission, every investigational visit within the protocol is now be performed remotely (e.g. by phone) for all participants still active in the study by the investigational site staff. The investigational site will continue to monitor the health status of the participants by collecting information on general health status, Concomitant Medication and Adverse Events.

Page 41 of 69

M7.5 and M10.5 phone calls include a pre-diabetic questionnaire as recommended by the DSMB committee.

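### The SAP plans no by-arm summary of the gallbladder ultrasound, so new abnormalities not reported as adverse events, and the number of participants with both scans, would not be tabulated

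*SAP*

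**What the plan says.** Protocol 8.2 gives the two scans different purposes. Of the first it says "this is required during screening to exclude previous or active hepatobiliary diseases". The second "is repeated at the end of the treatment (M6 visit) to assess any emergent hepatobiliary abnormalities".

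The Schedule of Activities (Protocol 1.3) has a row "Gallbladder ultrasound" marked at screening and at week 39 or end of intervention. During the outbreak the on-site month 6 visit became a telephone call, and for the month 9 visit the schedule states: "All safety and efficacy measurements previously listed for the M6/end-ofintervention visit are to be performed".

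On analysis, Protocol 9.4.5 says "Vital signs, biochemistry and hematology parameters will be described by descriptive statistics" and adds adverse event tables; it does not name the ultrasound. SAP 4.3 introduces its list with "The safety data for this study is" and does not name the ultrasound in its readable text. SAP 8.8 states "All safety data will be summarized/analyzed by treatment group" and then has seven subsections: adverse events, laboratory, vital signs, physical examinations, anthropometry, ECG and the short nutritional assessment. The words gallbladder and ultrasound do not occur in the readable SAP.

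**The concern.** The end-of-treatment scan is a targeted safety test with a question of its own: did new hepatobiliary abnormalities arise on treatment? In a trial of two doses against placebo, that question is answered by comparing arms. Exclusion criterion 7k removes people with a history or active signs of biliary disease, apart from quiet post-cholecystectomy cases, so a new abnormality at the end scan should be fairly easy to interpret.

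Without a planned table, an abnormality that the investigator does not regard as clinically relevant stays out of every by-arm summary. The reader of the study report also cannot tell whether few biliary adverse events in an arm mean clean scans or missing scans.

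**Working it through.** No plan figure needs reproducing; the check is to follow a scan result through the two documents.

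1. **Is the second scan safety data?** Yes. Protocol 8.2 is the safety assessments section and states the purpose outright.

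2. **Does SAP 8.8 analyse it?** No. Subsections 8.8.1 to 8.8.7 are numbered without a gap, the contents page ends the safety section at 8.8.7, and none covers the scan. The text of SAP 4.3 breaks off after the ECG item, so a lost item there cannot be ruled out. That would not supply the missing analysis in 8.8.

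3. **Where does each result go?**
   - *New abnormality judged clinically relevant:* Protocol 7.1 says "Any new clinically relevant finding will be reported as an AE". Under SAP 8.8.1 it is treatment-emergent if its recorded onset lies between first dose and six weeks after the last dose, and it is then counted by arm, system organ class and preferred term.
   - *New abnormality not judged clinically relevant:* it falls under the general listing rule of SAP 8.2 and appears in no table.
   - *Normal end scan, or no end scan:* listing at most; no table separates the two.

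4. **What does that leave out?** For one arm, let S be the safety population and P the number with both scans. Among those P, let A have a new abnormality reported as an adverse event and B a new abnormality not so reported. The scan's question needs (A + B) / P. Its contribution to the adverse event table is A / S. Because A ≤ A + B and P ≤ S, A / S can never exceed (A + B) / P; the two are sure to agree only if B = 0 and P = S. The plan tabulates neither B nor P.

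5. **Can P be taken as equal to S?** Not safely. SAP Figure 1 has 77 per arm (231 / 3 = 77) and Protocol 9.2 plans on 64 per arm, an allowance of 77 − 64 = 13 per arm, or 39 in all. Protocol sections 5 and 9.2 expect losses above that allowance because of COVID-19. Those figures concern the walking-test endpoint, so they are only a guide to missing scans. They do show that P should be reported rather than assumed.

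The documents give no rate for new ultrasound abnormalities, so B cannot be estimated.

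**The case against.** The best defence is that hepatobiliary safety is already compared by arm. Reporting a new clinically relevant finding is a protocol rule, not a favour, and those events are tabulated by treatment group. SAP 8.8.2 adds baseline-to-end shift tables by arm for transaminases, alkaline phosphatase, gamma-GT and bilirubin. All remaining data are listed, sorted by treatment group. The table shells are in a separate document (SAP 1) and might include the scan.

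Much of this stands, and it rules out three stronger readings that a reader might infer:
- *That new abnormalities are never counted by dose.* Those judged clinically relevant are counted, through the adverse event tables.
- *That the SAP silently dropped a planned analysis.* Protocol 9.4.5 never planned one, so the SAP's list of changes had nothing to declare. The gap starts in the protocol.
- *That every participant has a scan before and after treatment.* That is the plan; withdrawals and remote visits mean that some may lack the second.

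The defence does not close the gap. Clinical relevance is each investigator's judgement. Biliary findings are not among the events of special interest, which are falls and orthostatic hypotension. Laboratory shifts need not reveal silent stones. A listing is not the by-arm summary that SAP 8.8 promises for safety data, and shells elsewhere do not replace a stated method. Nor does the silence of Protocol 9.4.5 settle it: the SAP already summarises physical examination and anthropometry, which that section also omits, and gives a subsection to a nutritional score summarised at baseline only.

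**Conclusion.** The point holds in a limited form. As written, the SAP gives no by-arm count of scan abnormalities not reported as adverse events and no number with both scans, so the stated purpose of the second scan is not met by treatment group. It is a completeness gap in the descriptive safety analysis, cheap to close, with no effect on the primary or key secondary analyses. Its size in participants is unknown.

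The conclusion rests on the readable SAP text. It depends mainly on section 8.8, whose numbering is unbroken, rather than on 4.3, where the text is damaged.

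**What to change.** Before unblinding, name gallbladder ultrasound as safety data in SAP 4.3 and add a subsection after 8.8.7. For the safety population, descriptively and by treatment group, it should give:
- the number with a screening scan, with an end-of-treatment or end-of-intervention scan, and with both;
- a screening-to-end shift table, or a new-abnormality table if almost all screening scans are normal, with a rule for participants who have had a cholecystectomy;
- the number and percentage with a new abnormality among those with both scans, and how many of these were also reported as adverse events;
- a by-subject listing.

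Confidence intervals for each dose minus placebo are optional, since SAP 8.8 is descriptive. The data are already to be collected, so the cost is one table. If results were captured as free text, they also need coding as normal, abnormal or new abnormality, done blind to treatment. The documents do not show how the result is recorded.
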